### **7.2.7.3. Statistical Hypothesis**

The objective of the current study is to test a system for near real-time monitoring of vaccination coverage, benefits and risks. As such, no formal statistical hypothesis testing will be done.

### **7.2.7.4. Sample size considerations**

We derived the margin of error at the 5% significance level (or the half width of the 95% confidence intervals) based on the Poisson distribution relative to the assumed incidence, expressed in %. We assumed incidence rates of 2/10,000py, 50/10,000py and 100/10,000py (which correspond to the range of incidence estimates obtained in POC1). The margin of error is presented as a function of person-time with person-time varying from 100,000 to 800,000 person-years ([Figure 1](#)). For reference, the expected annual number of person-years for the population of interest is +/- 37,000 in RCGP (one of the smaller POC1 databases) and is +/- 220,000 for SSI (one of the larger POC1 databases).

**Figure 1: Relative margin of error (5% significance level) assuming incidence rates of 2/10.000py, 50/10.000py and 100/10.000py by database size (person yrs)**

### 7.2.7.5. Statistical Methods

In POC1.2, the objective is near real-time visual monitoring of vaccination coverage, benefits and risks using aP vaccination as the test case. As such, we will monitor epidemiological measures including, vaccination coverage and incidence rates as they evolve over time. The monitoring will be facilitated through the use of a “Shiny” web-application [4] with a user-friendly interactive dashboard containing three monitoring tabs for visualization of coverage, benefits and risks. This dashboard will be interactive and allow for inter-country comparisons.

#### ***Coverage: bar charts with weekly number of administered doses extrapolated to the whole population***

The total number of doses  $n_{ij}$  (for dose 1, dose 2 and dose 3) given during week  $i$  in age group  $j$  will be calculated from each database. Then, the total number of doses will be extrapolated to the whole population as follows:

$$N_{tot_{ij}} = (N_{ij}/pop_j)^{-1}n_{ij} = w_{ij} n_{ij},$$

where  $N_{ij}$  is the number of active subjects in the database at week  $i$  and age group  $j$  and where  $pop_j$  is the number of subjects in the total population of same age group  $j$ . The number of subjects in the total population will be obtained from the National Offices of Statistics.

---

**Coverage: line plots with vaccination coverage (%) by year-month birth cohorts over time**

For every birth-month cohort, we will evaluate the vaccination coverage by dose over time (i.e. at every start of the week/month depending on the refresh frequency of the database). The coverage at week  $i$  for birth cohort  $j$  will be calculated by dividing the number of vaccinated subjects  $n_{ij}$  by the total number of subjects still under follow-up at week  $i$  ( $N_{ij}$ ), expressed as a percentage.

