## 2. ABSTRACT

Date of protocol abstract: December 11, 2017
Title: Testing a system for near real-time monitoring of vaccination coverage, benefits and risks in Europe with pertussis vaccines as a test case.
Rationale and Background: POC1.2 aims to test near real-time and visual monitoring of coverage, benefits and risks of acellular pertussis (aP) vaccination. POC1.2 is designed as a continuation of POC1 to leverage previously completed work. POC1.2 will use near real-time visual monitoring of aP vaccines in Europe as a test case, aiming to mimic the introduction of a new vaccine. The interactive dashboard developed as an additional analysis to POC1 will be regularly updated for monitoring.
Research Question and Objectives: The overall objective of the ADVANCE POC studies is to build and test a system (including data availability) for the benefit-risk monitoring of vaccines in Europe. The objective of POC1.2 is to determine the feasibility of periodic and rapid assessments of vaccine coverage, benefits and risks using electronic healthcare databases, while displaying these data using a dashboard. The specific objectives are to: 

1. Evaluate the ability of databases to generate periodic data with limited latency to secure near real-time monitoring on a preferably weekly basis (or bi-weekly/monthly if weekly would not be feasible)

2. Visually monitor vaccination coverage, benefits and risks using an interactive dashboard

Target Population: All children from their start of follow-up in the database until school-entry pertussis booster, 6 years of age or any periodic data lock point within the eligible ADVANCE databases.
Observation Period: The total observation period consists of two distinct periods. The first period starts from 01 January 2014 until the start of the near real-time monitoring upon approval of the protocol and has as objective to establish a baseline. The start of the first period (01 January 2014) was chosen to balance data accuracy and computational burden. The second period has the objective of near real-time monitoring and will cover a few months. This period will start upon protocol approval until last periodic data lock point (DLP) (i.e. the time the last periodic database extract is produced) and will cover a few months.
Study design: A dynamic cohort study

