#### **Data analyses**

The test case is near real-time (weekly or bi-weekly/monthly, depending on the database) visual monitoring of vaccination coverage, benefits and risks of pertussis vaccination. The monitoring will be facilitated through the use of an interactive dashboard developed based on the POC1 data. The dashboard contains three monitoring tabs with visualizations:

- Coverage: number of administered doses per week over calendar time (extrapolated to the population of interest) and vaccination coverage (%) within specific age groups by calendar time
- Benefits: observed pertussis incidence in the total population by calendar time
- Risks: incidence rates in event specific risk windows and in control periods (out of risk windows) at vaccination eligible ages, separately for each risk outcome by dose, estimated cumulatively over calendar time.

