#### **7.2.4. Study Population**

All children from start of follow-up in their database until end of follow-up within the eligible ADVANCE databases. Start of follow-up will be the latest of: start of the study (i.e. 01 January 2014), first date of registration in the database, date of birth. End of follow-up will be the earliest of: death, end of registration in the database or moving out, receipt of pertussis booster dose, reaching 6 years of age, or data lock point.

---

Prieto-Alhambra, D. et al. Relationship between mortality and BMI after fracture: a population-based study of men and women aged  $\geq 40$  years. *J. Bone Miner. Res. Off. J. Am. Soc. Bone Miner. Res.* 29, 1737–1744 (2014).  
Garcia-Gil, M. et al. Linking of primary care records to census data to study the association between socioeconomic status and cancer incidence in Southern Europe: a nation-wide ecological study. *PLoS One* 9, e109706 (2014).  
Incidence and risk factors for clinically diagnosed knee, hip and hand osteoarthritis: influences of age, gender and osteoarthritis affecting other joints. *Ann. Rheum. Dis.* 73, 1659–1664 (2014).

---

Children will be excluded if at least one of the following variables is missing: date of birth, date of start of follow-up (date the patient is entered into the registration system) and date of end of follow-up (e.g. end of registration, moving out, death, last data draw down - whichever is earliest).

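### Ending follow-up at the pertussis booster makes the dose 1–3 coverage curves fall falsely between booster age and age 6

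*Protocol*

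**What the plan says.** Section 7.2.4 defines start of follow-up as the latest of "start of the study (i.e. 01 January 2014), first date of registration in the database, date of birth". End of follow-up is the earliest of death, end of registration or moving out, "receipt of pertussis booster dose, reaching 6 years of age, or data lock point". The Abstract (section 2, Target Population) describes the same end point as "until school-entry pertussis booster, 6 years of age or any periodic data lock point".

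Section 7.2.7.5 (coverage line plots) states: "For every birth-month cohort, we will evaluate the vaccination coverage by dose over time". Coverage at week i is obtained by "dividing the number of vaccinated subjects" "by the total number of subjects still under follow-up at week" i. It makes no exception for children censored at booster and sets no upper age below the end of follow-up. The companion bar charts count doses given in each week "for dose 1, dose 2 and dose 3" and weight them by the number of subjects active in the database.

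The Abstract (Data analyses) describes the benefit measure as "observed pertussis incidence in the total population by calendar time". The Limitations (7.2.8) do not mention booster censoring.

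**The concern.** Censoring is harmless for a proportion only if it is unrelated to what the proportion measures. Here it is closely related: a booster is given mainly to children who already had the primary doses. Each booster takes a vaccinated child out of both numerator and denominator, while unvaccinated children stay to age 6. The remaining group becomes steadily less vaccinated through selection alone.

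Coverage is one of the three monitored quantities. Section 5 describes monitoring as a way to trigger an alert when the benefit-risk profile departs from expectation, and a fall produced by censoring looks the same on the dashboard as a real one. Section 7.2.7.5 also offers comparisons between countries, and section 7.2.6.2 refers to country-specific schedules. If booster timing differs by country, the artefact will start at different ages and could be read as a difference in coverage.

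**Working it through.** The protocol states no coverage value, booster uptake or booster age, so there is no figure of its own to reproduce. The definitions in 7.2.4 and 7.2.7.5 can be applied directly.

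**Inputs**
- p: true coverage of a primary dose in a birth cohort (assumed; range 85% to 97%).
- u1: share of primed children already boosted (assumed; range 50% to 95%).
- u0: share of unprimed children who have had a dose recorded as a booster (assumed; 0, or a quarter of u1).
- Numerator taken as vaccinated children still under follow-up, a subset of the denominator.

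**Formula.** After boosters, p(1 − u1) of the cohort is vaccinated and still followed, and (1 − p)(1 − u0) is unvaccinated and still followed. Therefore

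displayed coverage = p(1 − u1) / [p(1 − u1) + (1 − p)(1 − u0)].

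This equals p only when u1 = u0. It is below p whenever primed children are boosted more often than unprimed ones.

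**p = 95%, u0 = 0**
- u1 = 50%: 0.475 / (0.475 + 0.05) = 90.5%
- u1 = 85%: 0.1425 / (0.1425 + 0.05) = 74.0%
- u1 = 90%: 0.095 / (0.095 + 0.05) = 65.5%
- u1 = 95%: 0.0475 / (0.0475 + 0.05) = 48.7%

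**Some boosters in unprimed children.** With u1 = 90% and u0 = 22.5%: 0.095 / (0.095 + 0.05 × 0.775) = 0.095 / 0.13375 = 71.0%.

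**Sensitivity to true coverage (u0 = 0)**

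| True coverage | 50% boosted | 90% boosted | 95% boosted |
|---|---|---|---|
| 85% | 73.9% | 36.2% | 22.1% |
| 90% | 81.8% | 47.4% | 31.0% |
| 95% | 90.5% | 65.5% | 48.7% |
| 97% | 94.2% | 76.4% | 61.8% |

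At 95% true coverage, the curve drops below 80% only above about 79% uptake, and below 50% only above about 95%.

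**Which cohorts.** Children under 6 on 01 January 2014 enter, so births from January 2008 are included. Table 2 puts the monitoring in March to April 2018. The protocol does not state the booster age. Taking age 5 as a marker, births from January 2008 to about April 2013 are observed beyond it: 5 × 12 + 4 = 64 birth-month cohorts. For cohorts already at booster age on 01 January 2014, children boosted earlier never enter, so those curves are distorted from their first plotted week.

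**After the change.** If children are kept while alive and registered, numerator and denominator no longer depend on the booster. The plotted value is then p at every booster uptake, provided that leaving the database is unrelated to vaccination.

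**The case against.** The strongest objection is that follow-up in the coverage section may simply mean registration. The paragraph of 7.2.4 on missing dates illustrates end of follow-up by registration, moving out, death and last data draw, without the booster. The Enddate field of Patients.txt (Appendix 2) is described in the same way, and 7.2.9.1 calls that file's content start and end of follow-up. On that reading the denominator is already sound. This shows a real ambiguity, but an illustrative list and a field description do not override the explicit definition in 7.2.4, which names the booster.

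It can also be said that the effect is confined to the time between booster and age 6, that its size rests wholly on assumed inputs, and that the success criteria in 7.1 concern refresh rate, timeliness and acceptability, not coverage values. No hypothesis is tested (7.2.7.3), and the disclaimer (section 11) excludes regulatory or clinical use. All of this stands and limits the severity.

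Some stronger readings are tempting but not supported:
- A reader might infer that coverage could exceed 100%, because the numerator is not expressly limited to children still followed. Numerator and denominator carry the same week and cohort indices and the ratio is a percentage, so the numerator is naturally a subset.
- A reader might infer that the extrapolated dose counts are greatly inflated at booster age. The weight uses subjects active in the database, which need not mean under follow-up, and few first to third doses would be expected at that age.
- A reader might infer that a primary-series dose coded as a booster would lose its risk window. Appendix 2 permits booster codes, but nothing says that any of doses 1 to 3 carries one.
- A reader might infer that pertussis incidence is biased towards unprotected children. Restriction to pre-booster time is a stated scope, and unboosted children include primed ones. Only the label in the Abstract is inaccurate.

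**Conclusion.** The point holds. Applied as written, the definitions in 7.2.4 and 7.2.7.5 make the dose 1–3 coverage curves decline falsely from booster age to age 6, in every cohort where primed children are boosted more often than unprimed ones. The direction follows from the definitions and that one premise. The size does not come from the documents: at an assumed 95% true coverage the fall is modest at 50% booster uptake and severe only at high uptake, and it shrinks if unprimed children are also boosted. Curves before booster age are correct.

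The Abstract and 7.2.4 also describe the censoring booster differently, one as the school-entry booster and the other as a pertussis booster without qualification. Appendix 2 allows several booster codes, so the age at which the artefact begins depends on which text is followed.

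This should be fixed. It is not critical, because the feasibility criteria do not depend on the coverage values, but a test of a monitoring display should not generate its own downward signal.

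**What to change.** 1. In 7.2.7.5, state that coverage is not censored at booster. Denominator: children of the birth cohort alive and registered at week i, up to age 6 or data lock point. Numerator: those among them who have received the dose by week i.
2. In the bar-chart paragraph of 7.2.7.5, state that the count of active subjects is the same registration-based count.
3. Reconcile the booster wording of the Abstract with that of 7.2.4, so that one definition applies wherever booster censoring is kept.
4. Either relabel the pertussis measure in the Abstract as incidence in children before booster, or compute it without booster censoring.

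The cost is small: wording in the Abstract, 7.2.4 and 7.2.7.5, and a change to the R transformation program described in 7.2.9.2. No new data are needed, because Enddate in Patients.txt has no booster criterion. As a change to the protocol, it would follow the amendment route in 8.4.

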**Benefits: line plots with pertussis incidence and 95% confidence intervals over time**

The pertussis incidence (/100.000 person-years) will be calculated as the number of pertussis events divided by the total person-time at risk for week  $i$  multiplied with 100.000. Exact Poisson 95% confidence intervals will be calculated.

**Risks: line plots with incidence of risk outcomes inside and outside the risk window and 95% confidence intervals over time using accrued data**

The incidence rate (per unit person- years) for the risk outcomes within the pre-defined, outcome-specific risk windows will be estimated by week. In addition, the incidence rates will be estimated cumulatively over time, using all data accrued from the start of the study period until week  $i$  or

$$inc_i = \left( \frac{\sum_{i=1}^i n_i}{\sum_{i=1}^i py_i} \right) \times \text{unit person years}$$

where  $n_i$  is the number risk events of interest that happened during week  $i$  and where  $py_i$  is the amount of person-time (in years) within that week. Incidence rates outside the risk windows in vaccination comparable age groups will be calculated as well. Each time, exact Poisson 95% confidence intervals will be calculated.

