***Denmark: SSI/AUH\****

In Denmark national registry data are assembled and linked for specific studies according to the scientific question. Overall, the Danish Civil Registration System (CRS) database comprises individual level information on birth date, gender, vital status and sequential dates of migration of all residents in Denmark, i.e. approx. 5.6 mill. persons in a year, and an accumulated number of approx. 7.5 mill. persons over the period 1996-2014. Hence, using a unique personal identifier assigned to all Danish residents upon birth or immigration makes it possible to link the CRS with health care databases such as the Danish Vaccination Registry (DVR) and the Danish National Patient Registry (DNPR).

The national childhood vaccination database was established in 2000. This comprises information on all vaccinations administered to children below the age of 18 years, including vaccinations recommended by the Danish childhood vaccination programme, such as HPV, influenza etc. From November 2015, GPs and

---

others authorized to vaccinate have an obligation to record all vaccinations, and this information is now merged with data that were compiled before 2015 into the Danish Vaccination Registry.

The Danish National Patient Registry has recorded every inpatient hospitalization since 1977, and every outpatient and emergency room visit since 1995. For each admission, one primary and potentially several secondary diagnoses are registered, classified according to the *International Classification of Diseases, Eighth Revision* (ICD-8) until the end of 1993, and *Tenth Revision* (ICD-10) thereafter. In Advance this database is used to identify events.

While CRS and DVR are updated on a daily basis, DNPR have a delay of up to 3 months. The data are kept at the Research Services at the SSI from where access can be granted provided that the analysis has been reported and approved by the Danish Data Protection Agency. There is a long tradition of epidemiological studies in Denmark based on the health care databases that were proven valid for research.

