**Table S14.1: Patients.txt**

Name of the Variable	Description of the Variable	Format / Possible Values	Description of the Values
PatientID	Patient Identifier	any string maximum length: 32 characters	
Birthdate	Date of birth	YYYYMMDD.	
Gender	Gender	F M	Female Male
Startdate	Date from which the patient is eligible to be included in the study. This is typically the date the patient is entered into the registration system (date of registration with insurance/region, date GP started to collaborate). Run in periods should not be applied when defining StartDate	YYYYMMDD.	
Enddate	Date after which the patient is no longer eligible for inclusion in the study (e.g. end of registration with GP/database, insurance, moving out, death, last data draw down (whichever is earliest)).	YYYYMMDD.	

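### The most recent weekly incidence rates divide partly reported events by person-time up to the data lock point, so they are biased towards zero; SSI/AUH is the documented case

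*Protocol*

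**What the plan says.** Protocol section 7.2.7.5 plots weekly pertussis incidence as "the number of pertussis events divided by the total person-time at risk for week" i, with exact Poisson 95% intervals. Risk-outcome incidence is estimated by week and also cumulatively: "the incidence rates will be estimated cumulatively over time, using all data accrued from the start of the study period until week" i. In that formula the numerator term "is the number risk events of interest that happened during week" i, so events are placed by the date they occurred, not the date they were reported.

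Section 7.2.4 ends follow-up at the earliest of several dates, the last three being "receipt of pertussis booster dose, reaching 6 years of age, or data lock point". The abstract describes the last lock point as "the time the last periodic database extract is produced". Table S14.1 likewise lets a child's end date be the last data draw-down if nothing earlier applies. Neither is defined as the date to which events are complete.

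On the Danish data, section 7.2.3 says of DNPR: "In Advance this database is used to identify events". It then adds: "While CRS and DVR are updated on a daily basis, DNPR have a delay of up to 3 months".

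Section 7.2.5 sets at least 3 data loads and at most 3 months of monitoring. Section 7.2.7.2 will describe the distribution of reporting delays and split it into database-level and healthcare-level parts. Nothing in 7.2.7.5 uses that distribution, and the limitations in 7.2.8 do not mention incomplete recent weeks.

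**The concern.** An event that has occurred but is not yet reported is missing from the week it belongs to, while that week's person-time is already counted. At each refresh the right-hand end of a weekly curve is too low. It rises later as reports arrive, but a new set of low weeks takes its place. A viewer could take the fall for declining pertussis or declining risk, and a true increase could be hidden. Section 5 says monitoring should raise an alert when the profile departs from expectation, and the newest weeks are where that matters most. The Poisson interval describes random variation in the reported count, not the events still to come.

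**Working it through.** The protocol gives no figure for this bias, so there is none to reproduce. Its only lag figure is the DNPR maximum of 3 months. The delay shapes below are assumptions, chosen to show a range.

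**Completeness of recent weeks.** Let F(a) be the probability that an event has been reported within a days. With constant incidence and person-time complete to the lock point, the expected ratio of reported to true rate over the last w days is

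C(w) = (1/w) × integral of F(a) for a from 0 to w.

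- Uniform on 0-90 d: C(w) = w/180 for w up to 90. C(7) = 7/180 = 0.039; C(28) = 28/180 = 0.156; C(91) = (45 + 1)/91 = 0.505.
- Exponential with mean m: C(w) = 1 − (m/w)(1 − exp(−w/m)). For m = 14 d: C(7) = 1 − 2 × 0.3935 = 0.213; C(28) = 1 − 0.5 × 0.8647 = 0.568; C(91) = 0.846.

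| Assumed delay | Last 7 d | Last 28 d | Last 91 d |
|---|---|---|---|
| Uniform 0-90 d | 4% | 16% | 50% |
| Exponential, mean 30 d | 11% | 35% | 69% |
| Exponential, mean 14 d | 21% | 57% | 85% |
| Fixed 91 d | 0% | 0% | 0% |

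Even with delays uniform on 0-14 d, the last week shows only 3.5/14 = 25% of its events.

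**Intervals, Danish illustration.** Section 7.2.7.4 gives about 220,000 person-years a year for SSI, or 220,000 × 7/365.25 = 4,216 per week. At its middle illustrative rate of 50 per 10,000 person-years, 4,216 × 0.0050 = 21.1 events are expected per week. Under uniform delays on 0-91 d:

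- latest week: 21.1 × 3.5/91 = 0.8 events seen. With 1 event, the exact upper limit is 13.2 per 10,000 person-years.
- fourth-latest week: 21.1 × 24.5/91 = 5.7 events seen. With 6 events, the upper limit is 31.0 per 10,000 person-years.

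Both intervals exclude the true 50. At the lowest illustrative rate, 2 per 10,000, only 0.84 events are expected per week. Zero observed gives an upper limit of 8.75, which still contains 2, but only because the interval is so wide.

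**Cumulative risk curves.** For delays bounded well below the accrual time T, the expected shortfall is mean delay/T. From 1 January 2014 to an assumed lock point of 31 May 2018, T = 1,611 d. The shortfall is 7/1,611 = 0.4% (uniform 0-14 d), 45.5/1,611 = 2.8% (uniform 0-91 d) and 91/1,611 = 5.6% (fixed 91 d).

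**The case against.** - **One database, not six.** A reader might infer that outcome events arrive months late everywhere. The documents do not support that. Only DNPR has a stated lag; section 7.2.7.2 acknowledges delay elsewhere without sizing it. The objection stands and limits the documented case to SSI/AUH.
- **Person-time may stop earlier in practice.** Section 7.2.7.2 measures database-level delay from the latest end-of-follow-up dates in the population files, and Danish data are linked for each study. If a custodian set the end date to the last date of complete event data, the database-level part of the bias would shrink. Section 7.2.4 and Table S14.1 neither require nor exclude this, and healthcare-level delay would remain. It is a reason to state the rule.
- **The risk display is also cumulative.** A reader might infer that every risk curve will fall towards the present. The cumulative curves will not do so materially, because more than four years of accrued data dominate them. Rates inside and outside the risk window also share part of the lag, so their contrast is less biased than either rate. Both points stand for the cumulative and contrast displays, but pertussis is planned as a weekly rate only.
- **This is a feasibility study in which latency is under test.** There is no hypothesis test, the results are disclaimed for clinical and regulatory use, and the numerical success criteria in 7.1 do not depend on the displayed rates. That lowers the stakes. Even so, visual monitoring is the second objective, stakeholders judge the dashboard, and measuring delay does not correct what is plotted.
- **A separate SAP is scheduled and may deal with this.** It may add shading or a cut-off. But the protocol itself fixes the rate formula and the end of follow-up, and these produce the bias if followed as written.

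**Conclusion.** The concern holds for the weekly pertussis and weekly risk-outcome rates in the latest weeks before each lock point. For SSI/AUH the deficit could span the whole monitoring period, since the stated maximum lag equals its maximum length. The table's percentages rest on assumed delay shapes, constant incidence and person-time complete to the lock point. The direction of the bias needs only that some events are reported after their person-time is counted. For the other databases the direction is the same wherever this happens, but the size cannot be derived from the protocol. Cumulative risk curves are low by about 0.4% to 6% over the scenarios examined, which is minor.

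**What to change.** In section 7.2.7.5, for each database and event source:

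1. State the date to which events are regarded as complete. Set it from the known source lag (3 months before the lock point for DNPR) and update it with the delay distribution from 7.2.7.2.
2. For rates that are interpreted, count both events and person-time, inside and outside risk windows, only to that date.
3. Keep showing later weeks, shaded and labelled as provisional and not for interpretation.
4. Add the limitation to 7.2.8.

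Weighting person-time by the estimated probability of having been reported can be a secondary display where the delay distribution is well enough estimated. It should not be the main rule: the distribution may rest on as few as 3 loads over at most 3 months, which captures long delays poorly.

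The programming is modest; the real cost is a shorter interpretable curve. With a 91-day cut for DNPR and 13 weeks of monitoring, 91 − 91 = 0 monitored days are interpretable for Danish outcomes at the last lock point. That should be reported as a timeliness result under section 7.1.
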